9.4. Planned Interim Analyses (If Applicable)

N/A

9.5. Plans for Coping with Screen Failures, Withdrawals and Loss-To-Follow-Up

Participants will be screened for key eligibility criteria over the phone prior to the study visit. Only subjects that meet the key eligibility will be scheduled for a visit. If any eligibility criteria is not met on day of the visit (eg. Vital signs, spriometry results), subject will be considered a screen-failure and no additional procedures will be completed. Additional participants will be recruited to replace screen failures in order to meet target enrollment numbers.

Due to the short duration of the study, we do not except any withdrawal or loss to follow up patient. In the case a subject would withdraw consent, we will recruit another subject to reach our desired sample size for analysis.

9.6. Sample Size Rationale

Sample size:

Based on the results of mucociliary transport (MCT) rates (healthy: 6.58 ± 1.39 , *Rspn1*^{-/-}: 1.63 ± 0.78 , other PCD: 0) in our mouse model [13], we expect subjects with a mild genotype to average 25% of the MCC of healthy subjects (healthy: Ave60Clr = $14.3 \pm 7.2\%$; mild expected: $3.6 \pm 2\%$), while subjects with a severe genotype will not show any MCC results, i.e. Ave60Clr not different from 0 (expected 0.5 ± 0.25). With $n=10$, we will be able to observe significant differences between all groups, with $\alpha=0.05$ and power=0.8.

Moreover, we expect the mild genotype group to react to albuterol treatment by doubling their Ave60 Clr, while the group with severe mutations will not. With 10 subjects, we will be able to find a significant response in the mild genotype group with expected Ave60Clr = $7.2 \pm 4\%$. Accounting for 20% possible dropout, we plan to enroll 12 subjects.

10. Safety Monitoring and Management

10.1. Risk / Benefit Assessment

Potential Risks:

Potential Risks of Spirometry:

Potential risks include possible lightheadedness or wheezing.

Potential Risks of Mucociliary clearance scan:

The radiation risks for the MCC scan, including the Cobalt 57 transmission scan and the Americium241 disks, which are used as fiducial markers is approximately 44 mRems. Adults in the New York City area receive about 300mRems per year in natural radiation exposure.

Potential Benefits:

Potential Benefits includes looking at possible treatment to improve mucociliary clearance and/or cough clearance in patients with PCD.

10.2. Assessment of Safety

The study procedures are low risk and are not expected to cause any adverse events, however, to ensure that subjects are tolerating the study well we have listed the screening and assessments below. General screen including physical exam at the start of the study and symptom-based exams during the study.

- Spirometry will be completed at baseline and after administration of SABA.
- Pulse oximetry will be checked at the start of the study and as needed.
- Vital Signs will be obtained at the start of the study and as needed.

Protections to Minimize Risk of Spirometry:

- Subjects will be seated in a non-rolling chair when spirometry is performed and standard methodology conforming to the American Thoracic Society guidelines for measurement of spirometry will be used. Subjects will be instructed to notify the study staff if they feel lightheaded, and albuterol will be available in the event the subject experiences any unanticipated

bronchoconstriction.

Protections to Minimize Risk of Mucociliary clearance scan:

- Radiation history is collected. Any subject who will exceed Federal guidelines for safe annual exposure limits will not be enrolled.

10.3. Unanticipated Problems, Adverse Events, Serious Adverse Events

Definition of Adverse Event (AE) and Serious Adverse Event (SAE)

An adverse event for a given volunteer will be defined as failure of any of the safety criteria outlined above. Decrease in lung function (FEV1) greater than 20% will be considered an adverse event. Any symptoms that induce a volunteer to seek medical attention from any provider within 96 hours of a study visit will be considered an adverse event. A serious adverse event will be defined as any event that requires hospitalization or results in life threatening illness or injury, permanent (or likely to be permanent) illness or injury, or death if these events occur within 96 hours of a study visit (or if the clinical scenario leading up to hospitalization, illness, injury or death begins within 96 hours of a study treatment visit).

Grading criteria

In addition to determining whether an adverse event fulfills criteria for a serious adverse event or not, the severity of adverse events experienced by study participants will be graded according to the criteria set forth in the National Cancer Institute's Common Terminology Criteria for Adverse Events Version 4.0. This document (referred to herein as the NCI-CTCAE manual) provides a common language to describe levels of severity, to analyze and interpret data, and to articulate the clinical significance of all adverse events.

All adverse events whether or not listed in the NCI-CTCAE will be graded on a scale from 1 to 5 according to the following standards in the NCI-CTCAE manual (A semi-colon indicates 'or' within the description of the grade.):

Grade 1 = Mild; asymptomatic or mild symptoms; clinical or diagnostic observations only; intervention not indicated.

Grade 2 = Moderate; minimal, local or noninvasive intervention indicated; limiting age- appropriate instrumental ADL (preparing meals, shopping for groceries or clothes, using the telephone, managing money, etc.).

Grade 3 = Severe or medically significant but not immediately life-threatening; hospitalization or prolongation of hospitalization indicated; disabling; limiting self care ADL (bathing, dressing and undressing, feeding self, using the toilet, taking medications, and not bedridden).

Grade 4 = Life-threatening consequences; or urgent intervention indicated.

Grade 5 = Death related to AE.

Adverse Event/Serious Adverse Event reporting procedures: Any SAE's and UP's will be reported to the IRB and the Medical Monitor. The funding agency will be notified of any SAEs.

Medical Emergency procedures: There is a study physician available for all inhalation procedures. A code cart and Automated External Defibrillator (AED) are available in the event of a cardiopulmonary

event. Albuterol, both inhalers and nebulizers, are available in the event of bronchospasm. If a subject has an event that is does not immediately respond to care in the research lab, he/she will be transported via EMS to UNC Healthcare for treatment.

10.4. Safety Monitoring

[Discuss how, in what time frame, and by whom subject safety will be monitored and the real-time plan for responding to adverse reactions, injury, and new safety concerns. Include criteria to be used for early study stopping. In addition to real-time evaluation, include consideration for a DSMB, Safety Monitoring Committee, or **Independent Medical Monitor**, as applicable, and describe in detail what their obligations will be. For a multi-site study, describe centralized safety oversight of the sites and communication of safety and quality issues]

Medical Emergency procedures: There is a study physician available for all inhalation procedures. A code cart and Automated External Defibrillator (AED) are available in the event of a cardiopulmonary event. Albuterol, both inhalers and nebulizers, are available in the event of bronchospasm. If a subject has an event that is does not immediately respond to care in the research lab, he/she will be transported via EMS to UNC Healthcare for treatment.

Data Safety Monitoring Plan: Data is initially recorded on paper documents, and the documents are maintained in a binder which is kept in a locked research office of study staff. This data is then entered into REDCap by an initial data entry person, and confirmed by a second user.

10.5. Study Suspension / Early Termination of the Study

[Describe circumstances that may warrant suspension/termination, e.g., unexpected, significant or unacceptable risk to participants; incomplete or unevaluable data; determination of futility. Provide actionable study stopping rules.]

Criteria for safety of a given individual during the study which would suspend the individual from further participation in the study will include:

1. A 20% or greater decline in FEV1 from baseline
2. Symptoms of respiratory distress.
3. Heart rate, blood pressure, or respiratory rate increase of more than 30% from baseline values (established on the same day).
4. SpO2 < 90% for > 1 hour.

11. Supporting Documentation and Operational Considerations

11.1. Regulatory, Ethical, and Study Oversight Considerations

11.1.1. Informed Consent Process

11.1.1.1. Consent/Accent and Other Informational Documents Provided to Participants

Consent forms describing in detail the study intervention, study procedures, and risks are given to the participant and written documentation of informed consent is required prior to starting intervention/administering study intervention. The following consent materials are submitted with this protocol:

1. Consent and Assent form for research study

11.1.1.2. Consent Procedures and Documentation

Describe the procedure that will be used to obtain informed consent/HIPAA authorization and assent (if applicable): Initial contact with potential subjects will be phone or virtual meeting. The study will be described in detail to the subject, including why the study is being conducted, the medication being studied, the risks and benefits, and what is expected of the subject. Briefly, the subject will be informed that they will undergo a screening exam and lung function testing. Subject will inhale a radiolabel substance and undergo medical imaging to measure the clearance of mucus from the airways. Albuterol will be administered and lung function testing will be performed. The imaging will be repeated two more times. The study will be completed in one day and will last 6 hours. The major risk of the study is exposure from the imaging and inhaling the radiolabeled substance. Radiation history will be collected and if it is more than the allowable safety limit, the subject will be excluded. The major benefit is to understand how subjects with PCD clear mucus.

The subject will be given adequate time to read the consent, and consent will be obtained prior to any study procedures. Consent may take place on a separate day from the baseline procedures. Due to COVID-19, consent forms will be reviewed by phone or virtual visit prior to the day of procedure. Subject will sign on the day of the procedure.

For subjects between the age of 12-17 years old, an assent form will be provided with age appropriate language. A parent will need to sign a consent form for the subjects.

Who will obtain consent: Consent will be obtained by a study coordinator or a study physician.

Where will consent process take place: The consent process and review will take place over the phone or virtual visit due to COVID-19 precautions and limiting in person interactions. Patient will sign the consent form on the day of the study. This study will take place at the UNC Meadowmont/Eastowne location. If necessary, the UNC CEMALB, located in the Human Studies Facility of the US EPA on [name] in Chapel Hill will serve as an alternate location.

How will investigator assure that subjects comprehend the nature of the study, procedures, the risks and benefits: The subject will be encouraged to ask questions regarding the study and procedures. Open ended questions will be asked of the subject to solicit correct responses, to help ensure that the subject understands the study commitment, procedures and risks and benefits

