4.1 Treatment Design

Type of Design: Open label; two group study with healthy controls

Screening/Baseline: Participants will undergo a general medical screening visit to include vital signs, physical exam and pregnancy test (if applicable), then proceed with spirometry.

Intervention/Treatment

Participants will inhale aerosolized radiolabeled sulfur colloid ($Tc99m$ -SC) and will undergo gamma scintigraphy to measure mucociliary and cough clearance (MCC/CC) of the radiolabeled particles from the airways in both groups. During the first hour of MCC imaging patients will attempt to avoid coughing. Patients will then inhale 4 puffs of albuterol (90 mcg/puff via metered dose inhaler (MDI) with spacer) to assess the effect of beta-adrenergic stimulation on MCC over the second hour of MCC

imaging. After the two hours of MCC imaging patients will perform spirometry and directed coughing over a 30 minute period during which CC will be measured, again by gamma scintigraphy. Subjects will then rest (app 3.5 hours) and be scanned for 15 minutes at 6 hour \pm 30 minutes post initial MCC/deposition scan.

Table of procedures

| PCD MCC/CC study flow sheet | minutes needed | cumulative min |
|---|----------------|----------------|
| 1 Vital signs, PE,pregnancy test, PFT | 30 | 30 |
| 2 Put Americium fiducial markers on | 5 | 35 |
| 2 Co57 Transmission scan | 5 | 40 |
| 3 Background scan | 15 | 55 |
| 4 Radioaerosol inhalation | 5 | 60 |
| 5 MCC scan (no cough) | 64 | 124 |
| 6 Albuterol MDI (4 puffs with spacer) | 6 | 130 |
| 7 MCC scan post albuterol | 54 | 184 |
| 8 PFT and directed coughing (30 coughs including any spontaneous induced by PFTs) | 20 | 204 |
| 9 CC scan post PFT/cough | 4 | 208 |
| 10 Rest until final scan 6 hours after beginning of #5 | 210 | 418 |
| 11 6 hour post initial radioaerosol MCC scan | 15 | 433 |

Unscheduled Visits: There is no expectation for unplanned visits. Subjects will simply be rescheduled if they have a change in health.

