7.8. Premature Discontinuation

Study is considered completed after the last scan of the day. Subjects may withdraw at any time. Subjects may be withdrawn at any time for safety concerns. Subjects who have any unanticipated problems (UPs) with the study procedures will be monitored until resolution of the symptoms.

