9.2. Description of the Study Cohort

The study cohort will consist of 12 PCD subjects with mutations in genes associated with a mild pulmonary phenotype (RSPH1, RSPH9, RSPH4a, or DNAH11) and 12 PCD subjects with mutations in genes associated with a more severe pulmonary phenotype (DNAH5, DNAI1, CCDC39, or CCDC40). A subject with mild pulmonary phenotype will typically have later onset of respiratory symptoms, better lung function, and milder bronchiectasis [4]. The age of patients will range between 12-90 years old. Eight healthy patients will be enrolled and undergo the same MCC protocol to obtain data for comparison. All subjects following the protocol will be included in the database. Subjects not

completing the protocol will be replaced. Baseline measurements of population (age, gender, race, FEV1) will be tabulated, for the whole population and per group (mild genotype, severe genotype, healthy) using mean and standard deviation and frequencies with percentages as appropriate. Data will be plotted in graphical figures including as histograms, bar plots, and scatter plots.

9.3.Aim-Specific Plans

Aim 1: To estimate how MCC measurements vary in PCD subjects with mutations in genes that are associated with mild or severe disease, relative to healthy subjects, and compare the 3 populations in term of Average Clearance.

Aim 1 is measuring MCC in PCD subjects having confirmed mutations in genes associated with a milder clinical phenotype and subjects with PCD caused by mutations in genes associated with a more severe clinical phenotype. These measurements will be reported as estimates of the means and standard deviations of Ave60Clr for each group, with associated confidence intervals. The baseline MCC in PCD subjects with “mild genotypes” and “severe genotypes” will be compared to healthy subjects. Our expected result is that subjects with mutations in genes associated with mild disease will display lower MCC rates than healthy subjects, and subjects with mutations in genes associated with severe disease will be even lower. For this comparison, we will use an ANOVA followed by multiple comparisons, using the Tukey Kramer correction. Then, to control for other possible sources of variations, age, gender and the initial deposition C/P will be added as covariates to PCD groups in a linear regression model on MCC.

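### The consent description gives a 6-hour study, but the flow sheet runs to 433 minutes and every permitted schedule ends 45 to 105 minutes after the stated 6 hours

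*Combined protocol and SAP*

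**What the plan says.** Section 11.1.1.2 (Consent Procedures and Documentation) summarises the consent discussion. Under it, "the subject will be informed that they will undergo a screening exam and lung function testing". It goes on to the radiolabel inhalation and imaging, then albuterol and further lung function testing. It continues "The imaging will be repeated two more times" and closes the description with "The study will be completed in one day and will last 6 hours".

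The table of procedures in Section 4.1 (Treatment Design) gives minutes and cumulative minutes for each step of the day. The last step before the first MCC scan reads "4 Radioaerosol inhalation | 5 | 60", and the final row reads "11 6 hour post initial radioaerosol MCC scan | 15 | 433". The table times the final scan at 6 hours from the start of step 5, the first MCC scan. Sections 4, 4.1, 7.4 and 8 allow ±30 minutes around that time, and the final image takes 15 minutes.

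Sections 5.4, 7.3 and 11.1.1.2 have consent signed on the day of the study. The flow sheet allots no time to it.

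**The concern.** The 6-hour figure looks like the scan-to-scan interval reused as the length of the whole study. The description that carries it includes the exam and lung function testing, which take place before the first scan. It therefore cannot naturally be read as scanning time only.

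At stake is the accuracy of a stated commitment. Section 11.1.1.2 says the discussion will cover what is expected of the subject, and it plans to check that subjects understand the commitment. The subjects include minors aged 12 to 17 and the parents who consent for them. A duration that the protocol's own schedule cannot meet should not be in that description.

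**Working it through.** **Inputs.** Step durations come from the Section 4.1 table of procedures. The final-scan window (±30 min) and length (15 min) come from Sections 4.1, 7.4 and 8. The stated duration, 6 h = 360 min, comes from Section 11.1.1.2.

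**1. Reproduce the flow-sheet total.**

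30 + 5 + 5 + 15 + 5 + 64 + 6 + 54 + 20 + 4 + 210 + 15 = 433 min = 7 h 13 min.

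Every cumulative entry also checks: 30, 35, 40, 55, 60, 124, 130, 184, 204, 208, 418, 433. Against the stated duration, 433 − 360 = 73 min, and 73/360 = 20%.

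**2. Start of the first MCC scan.** 30 + 5 + 5 + 15 + 5 = minute 60.

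**3. End of visit under the window.** End = 60 + 360 + w + 15, where w is the departure from exactly 6 hours.

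| w (min) | Final scan starts | Final scan ends | Over 360 min |
|---|---|---|---|
| −30 | 390 | 405 (6 h 45 min) | 45 |
| 0 | 420 | 435 (7 h 15 min) | 75 |
| +30 | 450 | 465 (7 h 45 min) | 105 |

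The flow sheet starts the final scan at minute 418, which is 418 − 60 = 358 min after the first scan began. That accounts for 433 rather than 435 and lies well inside the window. Because the final scan is timed from the first, a change in the length of the albuterol, cough or rest steps does not move the end of the visit.

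**4. Can any permitted schedule fit 360 minutes?** At the earliest final scan, the time left before the first scan is 360 − (330 + 15) = 15 min. The background scan (15) and radioaerosol inhalation (5) alone need 20. If vital signs, exam, pregnancy test, spirometry, markers and transmission scan took no time at all, the visit would still last 20 + 330 + 15 = 365 min.

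**5. Where 6 hours does fit.** From the start of the first scan to the end of the last is 360 + w + 15 = 345 to 405 min. Six hours lies in that range, but this clock leaves out the first 60 minutes, which Section 11.1.1.2 counts as part of the study.

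**6. Imaging count.** The table has four scans after radioaerosol inhalation: steps 5, 7, 9 and 11. Taken row by row, three follow the first. If steps 5 and 7 are taken as one two-hour block, two follow it.

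**The case against.** The strongest reply is that Section 11.1.1.2 is a self-described brief summary, while Section 11.1.1.1 says the consent forms give the detail. The forms are not in the reviewed text and may already state the full visit length. This stands. It limits the finding to the protocol's own description: a reader might infer that all 32 participants are misinformed, and the documents do not show that.

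Three further readings are tempting and go too far.

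- **That the imaging count is plainly wrong.** Sections 4.1 and 7.4 treat the two hours of MCC imaging as one block, and Section 4 speaks of continuing the measurement after albuterol. On that reading the post-cough and 6-hour scans are the two repeats. The count is ambiguous, not in error.
- **That leaving out the directed coughs is an error.** A summary offered as brief need not list every manoeuvre.
- **That subjects will be lost.** Section 7.8 says "Study is considered completed after the last scan of the day", and Section 9.2 says that subjects not "completing the protocol will be replaced". Read literally, someone who left at minute 360 would miss a scan that opens at minute 390 and would be replaced. Nothing in the documents suggests that anyone would leave during a planned rest with a scan pending, and the same description says the study takes one day. A missed final scan would not touch the listed outcomes either: these use Ave60Clr, Ave120Clr and Ave150Clr. The aim-specific models adjust for age, gender and C/P, and Section 9.1 offers 6-hour clearance only as a possible covariate.

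None of this removes the mismatch in duration.

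**Conclusion.** The 6-hour figure in Section 11.1.1.2 is wrong as written when set against the protocol's own schedule. The flow sheet exceeds it by 73 minutes (20%), and the permitted range exceeds it by 45 to 105 minutes. Consent signing on the day can only add to this; the documents give no time for it, so it is left out of these figures.

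The result rests on three things: the flow-sheet durations, the timing of the final scan from the first MCC scan, and a clock that starts at the first procedure. The last follows from the description itself, which includes the exam and lung function testing.

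This is a correction to consent information. It has no bearing on power, sample size, type I error or the listed outcomes.

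**What to change.** Reconcile Section 11.1.1.2 with the Section 4.1 table of procedures. If the flow sheet stands, give the duration as about 7¼ hours from the first procedure to the end of the last scan, with a range of 6¾ to 7¾ hours, plus time for signing consent. Express it as elapsed time, not time on site, because the documents do not say that subjects must remain on site during the rest period. Check the consent and assent forms, and make the same change there if they carry the 6-hour figure.

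In the same edit, say whether the two imaging repeats count the post-albuterol scan as a separate session, and align the number with the flow sheet.

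The cost is a wording change, with a minor ethics-board amendment. No procedure or analysis changes. The one drawback is that the stated commitment becomes longer.

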11.2. Study Discontinuation and Closure

This study may be temporarily suspended or prematurely terminated if there is sufficient reasonable cause. Written notification, documenting the reason for study suspension or termination, will be provided by the suspending or terminating party to <study participants, investigator, funding agency. If the study is prematurely terminated or suspended, the Principal Investigator (PI) will promptly inform study participants, the Institutional Review Board (IRB), and sponsor and will provide the reason(s) for the termination or suspension. Study participants will be contacted, as applicable, and be informed of changes to study visit schedule.

Circumstances that may warrant termination or suspension include, but are not limited to:

- Determination of unexpected, significant, or unacceptable risk to participants
- Demonstration of efficacy that would warrant stopping
- Insufficient compliance to protocol requirements
- Data that are not sufficiently complete and/or evaluable
- Determination that the primary endpoint has been met
- Determination of futility

Study may resume once concerns about safety, protocol compliance, and data quality are addressed, and satisfy the sponsor, IRB and/or Food and Drug Administration (FDA).]

No adverse events are expected from the study procedures. Criteria for safety of a given individual which would suspend the individual from further participation in the study will include:

1. A 20% or greater decline in FEV1 from baseline
2. Symptoms of respiratory distress.
3. Heart rate, blood pressure, or respiratory rate increase of more than 30% from baseline values (established on the same day).
4. SpO2 < 90% for > 1 hour.

Criteria for safety within the entire protocol (failure of which would result in suspension of further study until consultation with the IRB) will include the following:

1. If 2 of the first 10 participants fail the individual safety criteria outlined above, the entire protocol will be suspended pending review by the IRB.
2. No occurrence of any Serious Adverse Event

Subjects will be under direct supervision throughout MCC measurements and will either have contact information for after-hours access to a study physician or the UNC Health 24 hour line.

Screen failure procedures. For subjects who do not meet enrollment criteria, all study related activity will stop once it is determined that the subject does not meet criteria.

